In ICUAW, affection to the lower extremity can be seen in 32.3%. Mainly due to prolonged periods of immobilization or sedation, that lead to atrophy and dysfunction in the quadriceps and gastrocnemius muscles. The consequences are reduced 6-minute walk test distance, reduced ability to perform activities of daily living, and reduced ability to return to driving and paid employment. In healthy individuals, strict bed rest causes a 1% decrease in muscle strength per day. Casting limbs such as in orthopedic injuries has been shown to result in 25% decrease in muscle strength in 7 days. Therefore, in ICU patients, this problem should be approached as prompt as admission. A recent systematic review (Qin ES et al) in 10 studies (n = 985) found that early mobilization decreased the incidence of ICUAW at hospital discharge, increased the number of patients who were able to stand, and increased the number of ventilator-free days during hospitalization. However, reduced hospital staff or increased burden can be a limitation for providing assisted mobilization.

A practical solution to address these limitations is the use of electrical stimulation (E-Stim). In this matter, AVAZZIA Inc. (Dallas, TX, USA) has created an E-Stim device (Tennant Biomodulator PRO) that works on a high voltage alternative pulsed current (HVAPC) to address lower-extremity muscle weakness, endurance, pain, and neuropathy. This technology works through a symmetric biphasic waveform that achieves deep stimulation of the muscle fibers. In our previous trial in ICU COVID-19 patients (NCT04685213, H-47781-A), we demonstrated HVAPC improves gastrocnemius muscle endurance without burnout of oxygen consumption. Other ICU studies (Nussbau et al.) have demonstrated E-Stim is feasible to preserve strength and muscle mass, and reduce muscle degradation leading to maintenance of functional capacity. Its benefit has been seen to be higher when placed in hams and calf muscles bilaterally, in a supine position, and administered 5-7 days a week or until extubation or hospital discharge. Another benefit has been linked to neural adaptations.

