E4. Neonates

Will neonates of uncertain viability or nonviable neonates (as described in 45 CFR 46 Subpart B) be enrolled in the research?

No

E5. Children

Will children be enrolled in the research?

No

Section F: Design/Procedure

F1. Design

Select one category that most adequately describes your research:

c) Pilot

Discuss the research design including but not limited to such issues as: probability of group assignment, potential for subject to be randomized to placebo group, use of control subjects, etc.

We will prospectively recruit 40 patients at risk of ICUAW. Sample size is convenient and designed to explore acceptability and feasibility of objective tools for measurement. Eligible participants will be screened at BSLMC. Those who satisfied the inclusion and exclusion criteria and signed the informed consent form will be randomly assigned with ratio of 1:1 into two groups. Consenting will be performed with a legal authorized representative (LAR) that is present. When the subject regains consciousness and is aware in time, space, and person, he/she will be re-consented. If the subject decline to continue participation in the study, the subject will be withdrawn. The informed consent will be obtained from all participants and their LAR.

Sub-population: Post-surgical patients that are admitted to the ICU will be consented either before surgery, or by a LAR on the day of surgery as described above.

The study will be double-blinded (clinicians and patients) in intervention (IG) and control (CG) group. Both cohorts will be followed-up and monitored at 3 days, and then weekly for a total period of 4 weeks or until hospital discharge, whichever comes first. • Intervention group (IG). The IG (n=20) will be undergoing E-Stim therapy with an active device during the hospitalization period until 4 weeks or discharge, whichever comes first. To deliver E-Stim, 2 electrodes will be placed in each proximal gastrocnemius and Achilles tendons. • Control Group (CG). The CG (n=20) will be undergoing E-Stim therapy with a placebo device (5-10% currents) as described in the IG.

Inclusion Criteria:

-Any patient older than 18 years old admitted to the ICU within two days. -Patient can be intubated with ventilatory assistance or not.

Exclusion Criteria:

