Neuropathy test: Sural nerve conduction/amplitude assessment (neuropathy, DPNCheck Device by Neurometrix Inc)

Biomarkers tests: Creatinine kinase, C-reactive protein, creatinine, potassium, myosin, serum lactate, arterial SpO2, duplex ultrasound for DVT will be collected from the electronic medical records. If biomarkers were not collected as a standard/regular procedure in the ICU; data will not be extracted from the electronic medical records. Research staff will not draw any blood samples.

Then, the patients will receive an individually programmed device to deliver neuromodulation to both gastrocnemius muscles simultaneously. The frequency of therapy will be 1 hour daily, and the duration will be up to 4 weeks or until hospital discharge, whichever comes first.

The coordinator will provide the ICU staff with a weekly spreadsheet showing utilization (therapy sessions/day) so compliance can be monitored. Also, the devices will monitor the time of usage to confirm hours of effective neuromodulation therapy to the skin.

Follow-up assessments will be performed at 3 days, and then weekly until 4 weeks or until hospital discharge, whichever comes first, by the research staff. The follow-up assessment will be identical to the baseline assessment.

In the final visit, we will assess muscle strength (ankle dynamometer, RoMech Digital Hanging Scale).

Additional measurements: - 1-month post-hospital discharge phone questionnaires: instrumental activity of daily living scale (IADL), community engagement (the Life Space Questionnaire), independence in daily living activities (KATZ), and anxiety (BAI).

Section G: Sample Size/Data Analysis

G1. Sample Size

How many subjects (or specimens, or charts) will be used in this study?

Local: 40 Worldwide: 40

Please indicate why you chose the sample size proposed:

Sample size is convenient and selected based on available resources to demonstrate feasibility and the proof of concept effectiveness of neuromodulation therapy for patients admitted to ICU and post-ICU. We plan to recruit 40 eligible subjects.

G2. Data Analysis

Provide a description of your plan for data analysis. State the types of comparisons you plan (e.g. comparison of means, comparison of proportions, regressions, analysis of variance). Which is the PRIMARY comparison/analysis? How will the analyses proposed relate to the primary purposes of your study?

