Statistical Design: Independent t-test, U-test, or Chi-square (depends on type of variables) will be used to compare between groups (IG, and CG for key baseline descriptors including demographics and relevant clinical characteristics). Those descriptors which showed statistical significant difference will be considered as covariates for adjusting the results in the following assessments. Appropriate mixed models (linear for continuous or Generalized Estimating Equations (GEEs) for non-continuous or non-parametric variables) will be used to test the intervention effect for each of the primary or secondary outcomes. Results will be adjusted by covariates as described above.

P-values of 0.05 or less will be considered statistically significant based on a two-sided test unless otherwise noted. All variables will be tabulated descriptively at each scheduled time point (baseline, follow up and discharge date). For each continuous variable, the analyses will include the mean, standard deviation, minimum and maximum. For each categorical variable, the summary will include frequencies and percentages. Each variable will be analyzed using all available data. Baseline variables will be summarized using descriptive statistics. We assume that a successful intervention is also helpful to maintain subjects muscle mass, reduce neuromyopathy signs and increase perfusion. The measured parameters (e.g. sEMG, US, strength, Kent imaging, DPN Check, etc.) should change substantially from baseline to the end of the intervention. For example, the EMG amplitude values should show increased voltages. Next, for all continuous variables, pre-treatment scores will be regressed on post-treatment scores to form residualized change scores (e.g. sEMG, US, strength, Kent imaging, DPN Check, etc.). Correlations will then be generated among these scores to determine whether changes in sEMG factors are related appropriately with increases in (clinically assessed) functional capacities and self-report measures of activities at 1 month post-hospital discharge. ANOVA test will be used to examine significant difference between patients with severe risk factors for prolonged ICU stage (e.g. age, BMI, cardiovascular morbidities). Moderator effects will also be examined for exploratory purposes.

Section H: Potential Risks/Discomforts

H1. Potential Risks/Discomforts

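### Change scores span follow-up of differing length and G2 ignores that length, so sEMG change can correlate with other measures through length of follow-up alone

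*Combined protocol and SAP*

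**What the plan says.** Section F2 says of the therapy that "the duration will be up to 4 weeks or until hospital discharge, whichever comes first". Assessments follow at 3 days and then weekly under the same stopping rule. Section F1 excludes only ICU stays shorter than 48 hours. The last assessment can therefore fall anywhere from about day 3 to day 28.

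G2 says that the measured parameters "should change substantially from baseline to the end of the intervention", forms residualized change scores from the pre and post scores, and continues: "Correlations will then be generated among these scores to determine whether changes in sEMG factors are related appropriately" to functional capacities and to self-reported activities 1 month after discharge. The general rule for significance is "P-values of 0.05 or less will be considered statistically significant based on a two-sided test unless otherwise noted".

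The only covariates that G2 admits are baseline descriptors that differ significantly between arms. Length of follow-up is not a baseline descriptor and cannot enter by that route. The mixed models are assigned to the intervention effect, not to these correlations.

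F2 places ankle strength at the final visit and the questionnaires once, a month after discharge. It describes no baseline for either.

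**The concern.** Two patients who lose muscle at the same daily rate get different change scores if one leaves on day 4 and the other stays 28 days. If several measures drift with time in hospital, the length of the window enters all of their scores at once. The scores then correlate even when a patient's rate of sEMG change says nothing about the rate of change in anything else. No treatment effect is needed for this.

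These are the only correlations in G2 that link sEMG change with function. The background proposes sEMG as an objective measure that does not depend on the patient being awake, and Section I lists a workable way of assessing neuromyopathy in hospital among the benefits. A significant correlation could be read as support for that use when it shows only that patients who stayed longer changed more on both measures.

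**Working it through.** The plan gives no expected correlation or power figure to reproduce. G1 says: "Sample size is convenient and selected based on available resources to demonstrate feasibility".

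**Inputs from the protocol**
- Sample size: "We plan to recruit 40 eligible subjects".
- Drift, from the background on healthy people: "strict bed rest causes a 1% decrease in muscle strength per day". Over 4 days this is 1% × 4 = 4%; over 28 days, 1% × 28 = 28%.
- Two-sided 0.05. At n = 40 this needs a correlation of about 0.31.

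**Assumptions, not in the protocol**
- Follow-up T uniform over 4 to 28 days.
- The same mean drift of 1 point per day in both measures (baseline mean = 100).
- Baseline SD 20.
- Daily rates independent between measures, with SD s.
- Measurement SD m at each visit.
- No treatment effect.

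**Formulas**
- Variance of T = 24²/12 = 48; mean 16; E[T²] = 16² + 48 = 304.
- Covariance between two measures through T alone = (mean drift 1) × (mean drift 2) × 48 = 48.
- Variance of a post-on-pre residual: V = 48 + 304s² + m² + 400m²/(400 + m²).
- Variance of a single later score: P = 400 + 48 + 304s² + m².
- Two change scores: r = 48/V.
- sEMG change against a single later score: r = 48/√(V × P).
- Regression as literally worded (pre on post), two change scores: r = (400/P)² × 48 / (400 + m² − 400²/P).

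For s = 0.5 and m = 5:
- V = 48 + 76 + 25 + 23.5 = 172.5, and P = 400 + 48 + 76 + 25 = 549.
- Two change scores: r = 48/172.5 = 0.28.
- Single later score: r = 48/√(172.5 × 549) = 0.16.

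The false-positive rates (FP) below are from simulation. The simulated mean correlations agree with the formulas to within about 0.02.

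| s, m | V | P | Two change scores: r, FP | Single later score: r, FP | Pre on post: r, FP |
|---|---|---|---|---|---|
| 0.3, 3 | 93.2 | 484.4 | 0.51, 94% | 0.23, 30% | 0.42, 76% |
| 0.5, 5 | 172.5 | 549 | 0.28, 41% | 0.16, 15% | 0.19, about 21% |
| 1.0, 10 | 532 | 852 | 0.09, 11% | 0.07, 10% | 0.03, about 6% |

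**Sign.** The numerator is a product of two mean drifts. If one is zero, the expected correlation is zero. If they have opposite signs it is negative, with the same size.

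**Other assumptions**
- Skewed stays (median about 10 days, limits 3 to 28) give 13% to 95% between two change scores.
- A second model works in SD units, with pre-post correlation 0.7 and uniform intervals of 3 to 28 days. Drift of 0.2, 0.3 and 0.5 SD per week gives 8%, 15% and 60% between two change scores, and 6%, 11% and 41% against a single later score. At 7% per week these drifts correspond roughly to between-patient CVs of 35%, 25% and 15% (7/35 = 0.20, 7/25 = 0.28, 7/15 = 0.47).
- At 0.1 SD per week or less the rate is about 5%.

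**After adding days of follow-up.** The mean correlation returns to about zero in every setting. With uniform stays, false positives fall to about 6% to 8% between two change scores (5% to 11% in another run) and to about 6% against a single later score. With skewed stays they are 5% to 14%. Some excess remains because patients differ in rate, so both scores still spread more widely at longer follow-up.

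**The case against.** A reader might infer from the 94% that the claim that sEMG tracks function would usually be false. The documents do not support that. Strength and the questionnaires have no described baseline, so no change score can be formed for them. The route is then length of stay acting on both sides, and under the main assumptions the rate is about 10% to 30%. The larger figures belong to sEMG against ultrasound or nerve measures. This objection stands in full.

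The drift is also borrowed. The 1% per day is strength in healthy people; the protocol gives no daily change for sEMG, muscle thickness, sural conduction or perfusion. G2 itself expects EMG voltage to rise with successful treatment. Measures moving in opposite directions would produce a negative correlation and could hide a real link. This stands too: neither size nor sign is fixed by the documents.

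G2 asks about change, not rate of change. If longer immobilisation causes muscle loss and then disability, total sEMG change does track function, and adjusting for time may remove real signal. Section I also hopes that the therapy will shorten stay, so follow-up length may itself be affected by treatment. This is a reason to show both correlations; it does not make the unadjusted one sufficient alone.

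Last, no aim or hypothesis in Section D rests on these correlations, and this is a 40-patient pilot. That limits the importance, but the remedy costs almost nothing.

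**Conclusion.** The point holds in a conditional form. The window differs by patient by design, the change scores and correlations make no use of its length, and the covariate rule cannot bring it in. Correlation through length of follow-up alone is therefore possible under G2 as written.

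With equal drift of 1% per day, uniform stays of 4 to 28 days, n = 40 and post on pre, false positives are about 11% to 94% between two change scores and about 10% to 30% between sEMG change and a single later functional score. With the regression direction as literally written, the first range becomes about 6% to 76%. That direction is a separate matter, and correcting it does not remove this one. The bias is negligible if drift is small or absent in one measure.

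A reader might also infer that the treatment comparison is compromised. This point does not reach it: the mixed models test the intervention effect separately. Nor does it show that any sEMG correlation found would be false, only that the planned analysis could not tell a real link from a shared time trend.

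**What to change.** In G2:
- Add days from baseline to last assessment as a term in the regression that forms each change score.
- Partial the same variable out of correlations with final-visit strength and the 1-month scales.
- Report adjusted and unadjusted correlations side by side, and do not claim that sEMG tracks function from the unadjusted one alone.
- Use permutation p-values for the small remaining inflation, shuffling only among patients with similar follow-up length. Free shuffling would ignore the wider spread that both scores share at longer follow-up.

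Optionally, repeat the correlations over a common window, baseline to the first weekly visit. This covers only the repeatedly measured tools and leaves out patients discharged earlier, so it is a check and not a replacement.

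The cost is a few sentences and one degree of freedom in 40 patients; visit dates supply the covariate. The downside is that adjustment may take out real signal that runs through length of stay, which treatment may affect. That is why both versions must be shown.

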Describe and assess any potential risks/discomforts; (physical, psychological, social, legal, or other) and assess the likelihood and seriousness of such risks:

The risk to participants of this study is considered to be minimal in a controlled environment with an attendant present. This research routine will not place subjects at higher risk than normal activities of daily living, and no more risk of harm or discomfort is associated with these tests than the discomfort normally incurred while performing normal muscle stretching. Subjects will be allowed rest time between trials as needed.

The devices and technology is completely non-invasive, safe, non-toxic and non-ionizing. The potential risks to subject are minimal. However, like any battery powered systems, there is a minimum risk of sensor malfunctioning. In addition, the

study devices are not waterproof, and although they use a low powered battery (similar to a cellphone battery), in order to avoid any risk of shock the monitor should not be submerged or saturated with fluids during operations or cleaning. It does not emit any radiation to the human body, and does not offer any significant risk to the subject.

Subjects may experience mild discomfort from the sensor on their legs. We will inform the subject to please notify the investigators if the sensor is uncomfortable.

All information we will collect about the subject will be stored in a secure location and coded in a way to maintain confidentiality. Only study personnel will have access to their records. Data collected during the study may be published and made publicly available. Data may also be shared with other research groups. However, data that could in any way identify them will not be made public or shared.

Some of potential risks of using neuromodulation therapy could be: * Skin related discomfort, such as tingling * Skin reaction to adhesive patch.

Some of potential risks of using DPN Check could be: * Skin related discomfort, such as tingling *

If the tingling sensation is too intense for the participant, they have the ability to reduce the intensity for their best level of comfort.

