Also, participation may help the investigators design a practical assessing method to identify the impact of neuromyopathy in the hospital setting and the prevention or reduction of post-ICU syndrome. This may allow physicians to provide personalized care by monitoring muscle loss and limb complications caused by prolonged hospital length of stay.

Describe potential benefit(s) to society of the planned work.

As described above, this work may allow physicians to provide more personalized care for hospitalized patients in need of physical therapy for continuous and prolonged periods, specially when having a severe illness.

Do anticipated benefits outweigh potential risks? Discuss the risk-to-benefit ratio.

This study brings no more than minimal risk to subjects as it only involves a non-invasive device. There are some risks associated with lack of comfort from neuromodulation, skin allergy to the neuromodulation sticky patches/electrode pads that are used for delivering neuromodulation therapy, risk associated with electrical mal-function of neuromodulation, and other unknown risks. All neuromodulation devices will be checked before any use to minimize the risk associated with electrical malfunction. All neuromodulation devices are FDA approved for the purpose of pain reduction and have been used for lower extremity muscle weakness prevention in our previous trial for ICU COVID-19 patients (Zulbaran-Rojas et al, *Frontiers in Medicine*, 2022). However, these devices have not been used before for purpose of reducing or preventing post-ICU syndrome. Although there is no direct benefit for participating in the study, their participation may help the investigators design a practical assessing method to identify the impact of Neuromyopathy in the hospital (ICU) setting.

Section J: Consent Procedures

J1. Waiver of Consent

Will any portion of this research require a waiver of consent and authorization?

No

J1a. Waiver of requirement for written documentation of Consent

Will this research require a waiver of the requirement for written documentation of informed consent?

No

J2. Consent Procedures

Who will recruit subjects for this study?

PI
PI's staff

Describe how research population will be identified, recruitment procedures, any waiting period between informing the prospective participant and obtaining consent, steps taken to minimize the possibility of coercion or undue influence and consent procedures in detail.

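### Pad skin reactions and electrical malfunction are named as risks, but no planned data item records them, and the stated discomfort routes do not serve intubated patients

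*Combined protocol and SAP*

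**What the plan says.** **Named risks.** H1 lists "Skin reaction to adhesive patch" among the risks of the therapy. The risk-benefit text in Section I adds "skin allergy to the neuromodulation sticky patches/electrode pads that are used for delivering neuromodulation therapy" and "risk associated with electrical mal-function of neuromodulation, and other unknown risks".

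**Discomfort.** After mentioning mild discomfort from the leg sensor, H1 says "We will inform the subject to please notify the investigators if the sensor is uncomfortable". Later, directly after the DPN Check risk list, it says of participants who find the tingling too intense that "they have the ability to reduce the intensity for their best level of comfort".

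**What is collected.** F2 lists surface EMG, calf muscle ultrasound, near-infrared perfusion of the plantar foot, a sural nerve test, chart biomarkers with duplex for DVT, ankle strength at the final visit and telephone questionnaires one month after discharge. The baseline set is repeated at day 3 and then weekly. For the chart items, "If biomarkers were not collected as a standard/regular procedure in the ICU; data will not be extracted from the electronic medical records". For use of the therapy, "the devices will monitor the time of usage to confirm hours of effective neuromodulation therapy to the skin".

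**What is analysed.** G2 covers baseline comparisons, models for the primary and secondary outcomes, correlations of change scores, an ANOVA by risk factors and moderator effects. It has no safety or tolerability summary.

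**Who is enrolled.** F1 admits patients whether or not they are intubated. E2 describes intubated patients as cognitively impaired and takes consent from a legal representative until they regain awareness.

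**Other safeguards.** Section I says "All neuromodulation devices will be checked before any use to minimize the risk associated with electrical malfunction". H1 assumes a controlled setting with an attendant. F1 excludes active lower-extremity wounds and conditions that clinicians judge to raise the risk of the therapy. H2 answers No to greater than minimal risk, and no monitoring plan follows.

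**The concern.** The plan names specific device harms and then has no place to write them down. A pilot on feasibility and acceptability should be able to say how many patients in each arm had a pad reaction or a device fault. Followed as written, this one could not, and an absence of reports could be misread as good tolerability.

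The gap matters most for patients who cannot speak for themselves. The background text already rejects measures that need an aware patient and asks for ones that do not depend on patient status. That reasoning is applied to efficacy but not to tolerability. Section I also says that the devices have not been used before to reduce or prevent post-ICU syndrome, so tolerability data here would be worth having.

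**Working it through.** The documents give no figure to reproduce: the sample of 40 is one of convenience, and no adverse-event rate is stated. The check is a matching of named harms to data items, followed by simple counts.

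**Step 1. Match each named harm to a data item (H1 and Section I against F2 and G2).**
- *Skin reaction or allergy at the pads.* The electrodes sit on the proximal gastrocnemius and Achilles tendons (F1). EMG and ultrasound examine the calf but report endurance and thickness. The perfusion camera images the plantar foot, which is not where the electrodes are. The nerve test, biomarkers and DVT duplex do not show pad reactions. No item fits.
- *Electrical malfunction.* The device log gives time of use, not why use stopped. The pre-use check comes before any fault that arises during use, and no record of it is specified. No item fits.
- *Other unknown risks.* There is no adverse-event item.
- *G2.* Its frequencies and percentages reach only variables that are collected. The E2 and J2 provision for sending critical information to the medical record is not tied to a study data item. Perceived acceptability in Section D is hypothesised for the intervention group only.

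**Step 2. Match the discomfort routes to the patients.** One route asks the patient to notify the investigators and the other lets the patient lower the intensity. By their position in H1, the first may concern the leg sensor and the second the DPN Check test. Whichever devices they cover, an intubated patient without awareness can use neither. An awake patient can use both. The documents do not give the intubated fraction.

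**Step 3. Exposure, as maxima only.** Inputs: 1 hour daily for up to 4 weeks (F2), and 20 patients per arm (F1).
- Active arm: 20 × 28 = 560 sessions.
- Both arms: 40 × 28 = 1,120 sessions.

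These hold only if every patient stays four weeks; therapy stops at discharge. They count all patients, not only those who cannot report.

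**Step 4. What recording would allow.** Exact (Clopper-Pearson) 95% limits for x of n = 20 patients affected: the lower limit is the 0.025 quantile of Beta(x, n − x + 1), and the upper limit is the 0.975 quantile of Beta(x + 1, n − x). For x = 0 the lower limit is 0 and the upper is 1 − 0.025^(1/20) = 0.168.
- 0 of 20: 0 to 16.8%
- 1 of 20: 0.1 to 24.9%
- 2 of 20: 1.2 to 31.7%

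The chance of at least one recorded event among 20 patients is 1 − (1 − p)^20. For assumed per-patient rates of 2%, 5%, 10% and 15% (not in the documents) it is 33%, 64%, 88% and 96%.

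**Step 5. Coverage of visit-based recording.** If weeks are counted from baseline, follow-up falls on days 3, 7, 14, 21 and 28. That is 5/28 = 18% of therapy days. With baseline, the maximum is 40 × 6 = 240 inspections. The Step 4 intervals would therefore describe events seen or reported at visits, not the full reaction rate.

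**The case against.** The strongest reply is that this is a small pilot declared minimal risk, with a device described as FDA approved for pain and already used by this group in ICU patients. The plan is not without safeguards. An attendant is assumed, active leg wounds are excluded, clinicians can exclude anyone at raised risk, and each device is checked before use. None of these needs an aware patient. Some enrolled patients will be awake, surgical patients may consent beforehand, and those who regain awareness are informed and re-consented. All of this stands as risk reduction. None of it assigns anyone to observe the electrode sites or to record a reaction or fault, and a minimal-risk answer in H2 does not create a record.

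Four stronger readings are tempting and are not supported.
- *No one watches patients who cannot report.* The attendant wording counts against this. What is missing is a stated duty to inspect and record.
- *The plan relies on self-report to detect pad allergy or malfunction.* The two H1 sentences concern discomfort and tingling, perhaps from other devices, and the stated measure against malfunction is the pre-use check.
- *Unrecorded faults would corrupt the Aim 1 adherence result.* Section D counts one hour on at least 4 days a week as adherent, so with daily therapy 7 − 4 = 3 sessions in a full week can be lost without changing the classification. A session lost to a fault is also real non-delivery, and a per-visit item would not separate causes session by session.
- *Serious harm is likely, or the H2 answer is wrong.* The documents give no event rate, and nothing here shows either.

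It is also fair to say that 0 of 20, with an upper limit of 16.8%, would not establish good tolerability. It would be a bounded statement where now there is none.

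**Conclusion.** The point holds as an omission in data collection. Pad skin reaction or allergy and electrical malfunction are named risks, no F2 or G2 item records them, and no by-arm tolerability result is planned. The discomfort routes in H1, whichever devices they cover, do not serve patients who are intubated and unaware.

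The size cannot be put as a number of missed harms, because neither a reaction rate nor the intubated fraction is given. It is the difference between no reportable interval and one such as 0 to 16.8% for 0 of 20, over at most 560 active sessions. The efficacy analysis is not affected. The change should be made because it is cheap and bears on patients who may be unable to report.

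The conclusion rests on the text available. The front pages and the consent form could not be checked; wording there could add instructions to patients but would not change what F2 and G2 list.

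**What to change.** 1. **F2.** At baseline and each existing follow-up visit, in both arms, research staff inspect the electrode sites and record presence and severity of any skin reaction, with baseline as the reference. Keep the inspection at the same point of each visit relative to the 5-minute stimulation. Add a short item on device malfunction and any other adverse event since the last visit.
2. **G2.** Tabulate patients affected by arm with exact 95% intervals, described as events seen or reported at visits. The control device runs at 5-10% current with the same placement, so a by-arm table may help to separate adhesive reactions from effects of the current.
3. **H1.** State that staff observation replaces self-report in patients who cannot report, and say which devices the notification and intensity sentences cover.

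**Cost.** One short form section and a few minutes at visits that research staff already make; no extra staff or visits. Brief reactions between visits can still be missed. Visible redness may hint at the arm, although the follow-up assessments already have research staff examining the calf for EMG and ultrasound.
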